Organizational structure of the team	
Translation, Recruitment, Training, and Ethics/Research Committee Approval. Contributions to Data Collection, Analyses, Interpretation, Writing, and Dissemination Activities.
 
CCIHP Site Principal Investigator: [name], MSc Research Assistants (Total = 1)
 
Emory University IRB Approval, Contributions to Data Collection, Analyses, Interpretation, Writing, and Dissemination Activities.
 
Emory University Principal Investigator: [name] Co-Investigator: [name] Consultant: [name]

Setting and location	
Setting. The undergraduate system in Vietnam is a suitable context for adapting the program, given its similarities with the US context where the program originated. Undergraduate study is 4–6 years, with two foundational years and 2–4 years for specialization. Except for political education and national defense, universities design their own curricular and extra-curricular activities and maintain networks through the Ministry of Education and Training (MoET), professional associations, and Youth Union, all potential pathways to bring the program to scale in the future.
 
Study site. The sites for this project are Hanoi Medical University (HMU) and Thang Long University (TLU), both in Hanoi. HMU is a 100-year-old state school with dental, medical, nursing, nutrition, public health, and paramedical/ ophthalmology technical programs. Its 1000 enrolled students are 40% men. TLU is a 24-year-old private university with 15 departments (e.g., math, business administration, social sciences). Its 7000 enrolled students are 45%-50% men. Both schools have provided letters of support for adaptation of the program with their students.

Quantitative Study Population	
Men 18–24 years and identifying as heterosexual or bisexual and enrolled at HMU and TLU as freshmen on 9/1/2019 are eligible.

Recruitment

Study design. Based on learning from the qualitative work, we will conduct a RCT with eligible college men to test the impact of the program on promoting prosocial bystander behavior and preventing sexual violence perpetration, through improvements in the seven knowledge, attitudinal, and emotional mediators over a seven month study period, with a baseline survey and two follow-up surveys 0 and 6 months post-intervention. Figure 1 depicts the basic RCT design.

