Survey sample and power. Men 18–24 years and identifying as heterosexual or bisexual and enrolled at HMU and TLU as freshmen on 9/1/2019 are eligible. According to recent enrollment figures, about 890 men matriculate yearly at HMU and TLU. Given a cooperation rate of 67% in similarly focused research among male Atlanta-based undergraduates,⁶⁸ this pool is sufficient to recruit a sample of 400 freshman men for participation in this study.

We computed the required sample sizes to detect our hypothesized effects with a power of .80. We used a Monte Carlo approach⁹¹ to calculate the required sample sizes 1) assuming an attrition rate of 30%; based on 2) Cohen’s medium-to-large-effect-categorization⁹² with regards to the proportion of the variance accounted for, R², by the model (.13 and .26) using corresponding values for a and b;⁹³⁻⁹⁵ and 2) a desired power level of .80. The computer program, Mplus,⁹⁶ was used to complete the computations.

To recruit students, CCIHP personnel will contact department chairs at each university to discuss the study with them. With their agreement, CCIHP will talk with faculty about the study and ask them to announce it in their classes using a flyer with a brief, standard project description. The department chair will obtain email and phone numbers of students. The team has used this strategy successfully to recruit undergraduates. The study staff will utilize student phone numbers to contact students to make sure they check their emails.

Field Methods

Data collection overview. After consent, participants will be assigned randomly, with an equal allocation to Real-Consent or a health-education

control program, using block randomization with random block sizes. Participants and analysts will be blinded to assignments.

Outcomes will be assessed at baseline, posttest (just after finishing the last module), and six months (Table 2). We will consider confounders and modifiers, like social desirability, emotional adjustment, sensation seeking, sexual behavior, aggressive peers, peer and social network diversity, peer social support, witnessing family violence, family cohesion, and social support (Table 2). Questions will model others in the field.⁶⁸

Table 2. Primary (Behavioral) and Secondary (Knowledge/Attitudinal/Emotional) Outcomes at Baseline, Posttest, and Six-Month Follow-Up				
Construct	Scale	Sample item	#	Resp
Primary Outcomes				

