Bystander self-efficacy	ROLB self-efficacy to intervene in SV ¹⁰¹	When I hear a sexist comment I indicate displeasure	8	1-7
Bystander intervention	ROLB self-behavior subscale ¹⁰¹	walk into my room & roommates are watching porn	5	1-7
Intimate Partner Violence	Revised Conflict Tactics Scale (CTS2) SV ¹⁰²	Used force to make partner have sex	7	1-6
Sexual Violence	Sexual Experiences Survey Rev. (SES-R), SV ¹⁰³	put my penis, fingers, objects into so's butt w/o...consent	8	0-3
Secondary Outcomes (Knowledge, Attitudinal, Emotional Mediators)				
Knowledge of law	Knowledge of legal defs of assault/rape scale ¹⁰⁴	Sex intercourse w/so <16 [is legal if] he/she gives consent	9	T/F
Knowledge of consent	Knowledge of informed consent to have sex ⁶⁸	If a woman dsn't physically resist sex, she has given consent	14	T/F
Norms degrading wn	ROLB other-behavior subscale ¹⁰¹	Rmate suggests...give alcohol to your date to 'loosen her up'	5	1-7
Gender attitudes	Hostility Toward Women Scale ^{105,106}	...many times women flirt w/men just to tease/hurt them	10	T/F
Gender attitudes	Hyper-Gender Ideology Scale short form (HGIS) ¹⁰⁷	If men pay for a date, they deserve smthg in return	19	1-5
Rape attitudes	College Data Rape Attitude & Behavior Survey ¹⁰⁸	...sex jokes and innuendos are only fun & harmless	20	1-5
Rape attitudes	Illinois Rape Myth Acceptance (IRMA) ⁴⁸	Rape happens when a man's sex drive gets out of ctrl	17	1-5
Dating violence attitudes	Attitudes Toward Male Dating Violence Scale ¹⁰⁹	A guy should not insult his girlfriend	39	1-5
Empathy for rape victims	Rape Empathy Scale (RES) ⁵⁴	In general,...rape is not...provoked by the rape victim	19	1-5
Control Variables				
Alcohol use	National College Health Assessment Survey ¹¹⁰	# drinks consumed when last partied	1	#
Sexual behavior	Safe Sex Behavior Questionnaire (SSBQ) ¹¹¹	engage in sex intercourse on the first date	7	1-4
Sexual communication	Communication self-efficacy ¹¹² (to discuss sex)	can discuss...using condoms w/any sex partner	4	1-10
total items and time required			192	42 m

Note. SV = sexual violence; α indicates the reliability of the scale in other samples.

Informed Consent

Assurances, IRB approvals, and oversight: Our ethics protocol will follow WHO guidelines for research on violence against women.¹³¹ Ethical approval will be sought from CCIHP, Emory University, and Georgia State University. Team members have completed certification training in research ethics.

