We then will assess the impact of the program on our main outcomes (H2, H3). With reference to Figure 2, each of these relationships is captured by the product of the two paths, ab , or the indirect or mediating impact of the program on our primary outcomes, transmitted through the individual mediators. Testing the significance of each product allows us to assess the significance of each path. To test these mediated effects, we will use confidence intervals derived from the bias-corrected percentile-based bootstrap approach, a resampling technique, as the valid use of regular standard errors relies on the unrealistic normality assumption, given that the products of two normally distributed regression coefficients is not normally distributed in general.^{117,118} A consequence is that the power of the test is reduced.¹¹⁷ The bootstrap approach is suitable here, as it allows researchers to assess the test statistics associated with these mediated effects without knowledge of their true distributions.⁸⁹ The standardized indirect effect coefficients with confidence intervals will serve as effect size measures of the various mediation effects.

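### The H2/H3 mediation analysis does not say which wave supplies mediator and outcome, and perpetration reported at posttest predates completion of the program

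*Combined protocol and SAP*

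**What the plan says.** Under Recruitment (Study design) in the Quantitative Study Design, the trial is planned "over a seven month study period, with a baseline survey and two follow-up surveys 0 and 6 months post-intervention". Field Methods (Data collection overview) adds: "Outcomes will be assessed at baseline, posttest (just after finishing the last module), and six months (Table 2". The title of Table 2 puts both classes of outcome on the same schedule: "Primary (Behavioral) and Secondary (Knowledge/Attitudinal/Emotional) Outcomes at Baseline, Posttest, and Six-Month Follow-Up".

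Table 2 lists four primary outcomes:
- bystander self-efficacy, "ROLB self-efficacy to intervene in SV";
- bystander intervention, "ROLB self-behavior subscale";
- partner violence, from the CTS2 sexual violence items (sample item: "Used force to make partner have sex");
- sexual violence, "Sexual Experiences Survey Rev. (SES-R), SV".

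No recall window is given for any of them.

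Under Plans for analysis (Intent-to-treat analysis), H1 is tested by path a. H2 and H3 are tested by the product ab, "the indirect or mediating impact of the program on our primary outcomes, transmitted through the individual mediators". No wave is attached to the mediator or to the outcome, and the power paragraph names none. The only wave wording in the analysis plan is in the supplemental analyses of the program group, which compare pretest-to-posttest change in mediators and in outcomes across subgroups. Posttest outcomes are therefore used analytically at least there.

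**The concern.** Posttest leaves no time after the program. A perpetration item answered at that visit can only refer to acts that occurred before or during delivery. If the path model draws perpetration from posttest, it does not address what the completed program does to later behaviour.

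The mediation model has a second problem. Knowledge, attitudes and empathy measured at posttest come after the acts reported at posttest. An association between them may arise because what a man has done shapes the attitudes he then reports. That association would enter path b, and so ab, as though it were mediation. Since ab is the only planned test of H2 and H3, the main result is exposed.

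Leaving the wave open also allows it to be chosen once results are known.

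**Working it through.** **1. Is a wave named anywhere?** The study design, data collection overview, Table 2, power paragraph, intent-to-treat analysis, robustness checks and analytic-issues text were read for a sentence that ranks the follow-ups or assigns one to path a or b. There is none.

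**2. Time available.** Seven months minus six months leaves about 1 month between baseline and posttest (an inference from the stated period). None of it follows completion. Because no recall window is stated, posttest reports could also include acts from before baseline.

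**3. What can each primary outcome show at posttest?**

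| Outcome | Nature | Posttest as a test of the completed program |
|---|---|---|
| CTS2 sexual violence | reported acts | no |
| SES-R | reported acts | no |
| Bystander self-behavior | time frame not shown by the sample item | depends on item wording |
| Bystander self-efficacy | current state | yes |

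**4. How far could reverse influence distort ab?** This is an illustration; apart from the sample size, the inputs are assumptions.

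- Completers: 400 × (1 − 0.30) = 280, from the planned sample and assumed attrition.
- Treatment X is 0/1 with equal allocation. Posttest perpetration Y is standard normal and independent of X, so there is no program effect on it.
- Posttest mediator M = aX + rY + e, with var(e) = 1, a = 0.4 and r = −0.3. Men who report more acts then report less favourable attitudes.
- Two-sided alpha is 0.05 (the plan states none), and a and b must both be significant.

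Path a: z = a√n / (2√(1 + r²)) = 0.4 × 16.73 / (2 × 1.044) = 3.21. Power = Φ(3.21 − 1.96) = 0.893.

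Path b (Y on M given X): b = r/(1 + r²) = −0.3/1.09 = −0.275, with |t| = |r|√(n − 3) = 0.3 × 16.64 = 4.99. Power = Φ(3.03) = 0.999.

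Joint: 0.893 × 0.999 = **0.89**. The spurious indirect effect is 0.4 × (−0.275) = −0.11, offset by a direct path of +0.11, so the total effect is zero.

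Sensitivity to the reverse effect, same formulas:

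| r | power, path a | rejection, path b | joint |
|---|---|---|---|
| −0.3 | 0.893 | 0.999 | 0.89 |
| −0.2 | 0.907 | 0.914 | 0.83 |
| −0.1 | 0.915 | 0.384 | 0.35 |
| 0 | 0.917 | 0.05 | 0.05 |

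A simulation of 4,000 trials per row agreed to within about one percentage point.

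**5. Multiplicity, for scale only.** With one simple z-test per outcome at alpha 0.05 and outcome correlation 0.3, the chance of at least one false positive among four outcomes is about 17% at one wave. At two waves it is 24% to 31% for wave correlations from 0.9 down to 0.3 (29% at 0.6). Under independence the figures are 1 − 0.95⁴ = 18.5% and 1 − 0.95⁸ = 33.7%.

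**The case against.** The strongest reply is that the plan is silent rather than wrong. The title of Table 2 is a data-collection schedule. It does not say that H2 and H3 will be tested at each wave, that success at either would count, or that posttest mediators will be paired with posttest outcomes. Figures 1 to 3 were not available in the text reviewed and might show an order. This stands: the charge is that the waves are unspecified. A reader might infer that the plan commits to the wrong pairing or gives both waves equal rank, but the documents do not say so.

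A reader might also infer that posttest cannot inform H2 or H3 at all. That goes too far. Self-efficacy is a current state, and the time frame of the self-behavior items is not shown. H2 and H3 are worded as a tendency and a propensity, which could shift by posttest. The program has six sessions, so men are partly exposed before the last one; a posttest difference or null in perpetration would carry some information about partial exposure. Even so, for the CTS2 and SES-R it would not be the effect of the completed program, and the order of mediator and act would remain ambiguous.

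The planned propensity-score check on path b does not close the gap. It adjusts for observed covariates and cannot restore temporal order.

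**Conclusion.** The concern holds in this form: the waves for mediator and outcome in H2 and H3 are not specified, and for the two perpetration scales posttest is the wrong source for a confirmatory test. The omission and the timing rest on the text alone.

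The size of any bias is not known. The 89% figure depends on assumed values of a and r, a normally distributed outcome and a joint-significance test in place of the planned bias-corrected bootstrap; it falls to 35% at r = −0.1 and to 5% with no reverse effect. It shows that the problem can be large, not that it will be.

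The 17% against 24% to 31% comparison should not be read as this trial's error rate. Alpha and the correlations are assumed, and the planned tests are bootstrap intervals for ab, whose false-positive rate depends on whether a or b is zero.

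The data remain usable whatever is decided, so this should be corrected before analysis but does not undermine the design.

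**What to change.** In the analysis plan:

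- Name six months as the confirmatory time point for reported perpetration (CTS2 sexual violence, SES-R), and for bystander behaviour if its items ask about past acts.
- State the recall period for each wave. At six months it should not reach back before posttest. Give a calendar anchor for men who have no posttest survey.
- Estimate path a on posttest mediators adjusted for their baseline values. Estimate path b by regressing six-month outcomes on posttest mediators, with treatment in the model and adjustment for baseline mediator and baseline outcome.
- Report posttest perpetration descriptively. Bystander self-efficacy may be analysed at posttest if the plan says so in advance.

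This needs no new visit or participants: a few sentences in the plan and a change to survey wording. There are two real costs. The confirmatory analysis relies on the wave with the most attrition, although 30% is already assumed and response weighting is planned. The changed recall period also slightly reduces comparability with baseline scores. The lagged model corrects the order of measurement but does not randomise the mediator, so the planned confounding check on path b is still needed.

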	
(n=10) and women (n=10) to understand the social context of sexual violence in this setting, and focus group discussions (FGDs) with college men (n=12) and university stakeholders (n=12) to elicit feedback on the original program. From these data, we will create scripts in storyboard format of the adapted program. In step 2, we will conduct FGDs with college men (n=12) and university stakeholders (n=12) to elicit feedback on the storyboards and to refine the adapted Program to ensure acceptability. We will use grounded theory to analyze all transcripts inductively and deductively, identifying themes and patterns among themes and comparing the emergent theory with the underlying theory of change of the program. From the final storyboards, we will produce a web-based adaptation of the program in Vietnam. Finally, we will conduct a randomized controlled trial to test the impact of the adapted program (n=200), relative to a health-education control condition (n=200), on knowledge/attitudinal/emotional mediators, and in turn, on sexually violent behaviors, and prosocial bystander behavior in freshmen men attending two universities in Hanoi. Innovation and Long-term Impact. This project will be the first to adapt and to test the impact of a novel, theoretically grounded, web-based intervention to prevent sexual violence perpetration and to promote prosocial bystander behavior among young men for use in a middle-income country. If our project shows that the adapted program is effective cross-culturally, it will have exceptional potential for scale-up to prevent men's perpetration of sexual violence against women globally.

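### University is not stated as a randomisation stratum and is not named in any planned model: a small efficiency loss for path a, and a possible confounder of path b

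*Combined protocol and SAP*

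**What the plan says.** All references are to the Combined protocol and SAP, Quantitative Study Design.

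- **Sites (Setting and location).** "The sites for this project are Hanoi Medical University (HMU) and Thang Long University (TLU), both in Hanoi". The first is described as a century-old state health-sciences school with 1000 students, 40% of them men. The second is a 24-year-old private university with 15 departments and 7000 students, 45-50% of them men.
- **Allocation (Field Methods, Data collection overview).** Men are randomised "with an equal allocation to Real-Consent or a health-education" control program, "using block randomization with random block sizes". No stratification factor is named.
- **Covariates.** The same section lists ten possible confounders and modifiers, and Table 2 lists three control variables (alcohol use, sexual behaviour, sexual communication). University is in neither list.
- **Models (Plans for analysis).** H1 is tested by path a, and H2 and H3 by the product ab. Variables found imbalanced at baseline may be controlled for in path a. A propensity score for the mediator is added as a sensitivity analysis for path b and compared with unadjusted results. The balance check, the propensity score and the non-response weights all take their covariates from a Table 5, which is not found in the documents.

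**The concern.** A two-site trial in which site is known before allocation can block within site and carry site in the model at almost no cost. Neither is stated here. Two separate things are at stake.

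- **Path a and other arm comparisons.** Chance imbalance in university mix, and between-university variance left in the residual, add noise.
- **Path b.** Randomising the program does not randomise the mediators, as the plan itself acknowledges. If university influences both a mediator, such as knowledge of law or consent, and reported behaviour, part of the mediator-outcome association comes from university. That enters ab, the quantity on which H2 and H3 rest. Stratified allocation would not remove it; only the covariate does.

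The optional adjustment covers neither. It depends on observed imbalance, is limited to path a, and gives up the precision gain whenever the arms happen to be balanced.

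**Working it through.** **The plan's own figures.** The documents give no figure for site balance or site-related precision. The sample is "impact of the adapted program (n=200), relative to a health-education control condition (n=200"), so N = 400. Sample size was computed "to detect our hypothesized effects with a power of .80", "assuming an attrition rate of 30" per cent, so 400 × 0.70 = 280 are analysed. The 400 cannot be reproduced: alpha, the path values and the number of paths are not given, only R² "by the model (.13 and .26) using corresponding values for a and b". The point does not depend on it.

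**Site split.** None is stated for the trial. From the enrolment figures, HMU has 1000 × 0.40 = 400 men and TLU has 7000 × 0.45 to 0.50 = 3150 to 3500. Proportional recruitment would give 400/3900 = 10.3% to 400/3550 = 11.3% from HMU. I use p = 0.11, and p = 0.50 as the other extreme.

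**Balance without stratification.** The SD of the arm difference in HMU share is √[4p(1−p)/N].

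- N = 400: √(0.3916/400) = 3.1 points at p = 0.11; √(1/400) = 5.0 points at p = 0.50.
- N = 280: 3.7 and 6.0 points.
- Simulated unstratified blocks (sizes 4, 6 and 8 assumed) agree. The chance of a difference above 10 points is about 0.2% (HMU about 11%) and 4.7% (50%) at N = 400, and about 1% and 9% at N = 280.
- A one-SD imbalance shifts an arm difference by 0.031 × 0.3 = 0.009 SD to 0.050 × 0.5 = 0.025 SD. The standard error is 2/√400 = 0.10 SD.

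**Precision from adjusting (arm difference, path a).** Let d be the difference between universities in within-site SDs (assumed). The variance explained is R² = p(1−p)d²/[1 + p(1−p)d²]. Power after adjustment, starting from 0.80 at an assumed two-sided 0.05, is Φ[(1.960 + 0.842)/√(1−R²) − 1.960].

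| HMU share | d | R² | R² × 400 men | Power |
|---|---|---|---|---|
| 11% | 0.3 | 0.0088/1.0088 = 0.9% | 3.5 | 0.803 |
| 11% | 0.5 | 0.0245/1.0245 = 2.4% | 9.6 | 0.809 |
| 50% | 0.3 | 0.0225/1.0225 = 2.2% | 8.8 | 0.809 |
| 50% | 0.5 | 0.0625/1.0625 = 5.9% | 23.5 | 0.823 |

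**Stratifying versus adjusting.** In a simulation with 280 men, a 50:50 split and d = 0.5, power was:

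- 0.795 with neither;
- 0.803 with stratification only;
- 0.818 with adjustment only;
- 0.819 with both.

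Once university is in the model, stratifying adds about 1/N: 0.25% at 400 and 0.36% at 280. Stratifying without adjusting also leaves the model standard error slightly too large (0.123 against an empirical 0.121).

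**Path b.** Suppose university shifts the mediator by d and also shifts the outcome directly by d, in within-site SDs. Omitting it adds d × p(1−p)d/[1 + p(1−p)d²] to b, which is the R² expression above. The added slope is therefore 0.009 to 0.024 at 11% HMU and 0.022 to 0.059 at 50:50. The standard error of b with 280 men is roughly 1/√280 = 0.060, so the bias runs from about 0.15 to 1.0 standard error. If the lower planning R² of .13 is read as one squared path (an assumption), b is √0.13 = 0.36 and the bias is about 2% to 16% of it.

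**The case against.** The case for leaving this alone is substantial, and much of it stands.

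- **Validity of the arm comparison.** A reader might infer that missing stratification biases the trial. It does not. Unstratified 1:1 blocks are unbiased, and ordinary confidence intervals already allow for chance imbalance. With two sites and 400 men this is an acceptable design.
- **Absence from the models.** A reader might infer that no planned model contains university. The documents support only that none names it. The covariate list sits in a Table 5 we do not have.
- **Attrition.** A reader might infer that site-related dropout goes unadjusted. That cannot be shown. Weights will be built from baseline screening, socio-demographic and other control data, and enrolment at one of the two universities is itself an eligibility criterion, so university may well be included. No attrition rate by site is given.
- **Size.** The documents show that the institutions differ, not that their students differ on any mediator or outcome. The top figure of about 24 men needs both d = 0.5 and an even split, whereas enrolment suggests about 10-11% HMU.
- **Scope of the arithmetic.** The precision formula is for an arm difference on a continuous scale. It does not transfer directly to ab or to rarely reported perpetration.

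What the objection does not meet is path b. Randomisation gives no protection there, and the propensity-score sensitivity analysis helps only if university is among its covariates. Nor does optional, imbalance-triggered control of path a replace a pre-specified term. The plan itself expects the two sites to add diversity to the sample.

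**Conclusion.** The point holds as a minor design and pre-specification improvement. No university stratum is stated, and no model is committed to including university. For path a the loss is one of efficiency: 0.9-2.4% of variance at 11% HMU and 2.2-5.9% at a 50:50 split, or at most about 2 points of power from 0.80. Nearly all of that comes from the covariate rather than from stratified blocks. For path b, omission can bias the estimate and so distort ab. The illustrative range is from negligible to about one standard error, with the direction set by the signs of the two university effects.

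These sizes rest on an assumed university difference of 0.3-0.5 SD, an assumed split, a two-sided 0.05 level and, for path b, equal university effects on mediator and outcome. If university predicts neither, the gain is nil.

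**What to change.** 1. Pre-specify a university indicator in the path a and path b equations, the propensity score and the response-weight model, whatever the balance check shows. This can be done at any time before unblinding and delivers nearly all the benefit.
2. State whether allocation is stratified by university. If it is not, and randomisation is not yet fixed, run the random-size blocks separately within HMU and TLU.
3. Supply Table 5 or correct the references to it, so that the covariates for the balance check, propensity score and weights can be seen.

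The cost is one covariate (one degree of freedom per equation) and a second randomisation list. The sample size and data collection do not change.
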